2.10.3 Handling of missing values/censoring/discontinuations

Change from baseline will only be calculated for patients with both baseline and post baseline values as:

$$\text{Change from baseline} = \text{post baseline value} - \text{baseline value}.$$

In case of any post-baseline or baseline observation(s) is missing for any patient, the change of baseline value will be missing.

2.11 Safety analyses

As stated in the protocol (Section 10.5), the following secondary safety endpoints will be evaluated:

AEs suspected to be related to the crushed deferasirox FCT:

- Number and percentage of patients who experienced AEs suspected to be related to the study treatment up to 24 weeks including 30 day safety follow-up overall and by SOC, PT and severity (see [section 2.11.1](#)).

Overall safety of crushed deferasirox FCT:

- Number and percentage of patients with any AEs, SAEs, and AEs leading to discontinuation together with their severity up to 24 weeks including 30 days safety follow-up will be provided. Details regarding the analysis of AEs are described in [section 2.11.1](#).
- Absolute change from baseline over time will be provided graphically by box plots for serum creatinine, creatinine clearance, UPCR, total bilirubin, ALP, ALT, AST for each visit. Furthermore, shift tables using low/normal/high classification will be provided. Details regarding laboratory abnormalities are described in [Section 2.11.4](#). See [section 2.10.2](#) for the mapping of an unscheduled visit to a scheduled visit and box plots and shift tables will be generated for each scheduled visit only after mapping an unscheduled visit.

2.11.1 Adverse events (AEs)

All AEs recorded during the study are coded using the latest version of the medical dictionary for regulatory activities (MedDRA). Adverse events will not be assessed according to the common terminology criteria for AEs (CTCAE); instead, AE severity (mild, moderate, severe) will be used to report treatment-emergent AEs starting on or after the date of first study medication (including AEs that start within 30 days after the discontinuation of the study medication).

Frequency tables for treatment-emergent AEs will be presented. The summary tables will include the number of patients, and the percentage of patients experiencing the AE. Multiple occurrences of the same event in the same patient will be counted only once in the frequency tables. However, all adverse events will be included in the AE listings.

Frequency tables will display at least the MedDRA system organ class or preferred term, AE severity (mild, moderate, severe) or both, and relationship to study treatment. The following tables will be generated based on the data up-to 24 weeks including 30 days follow-up:

- Adverse events, regardless of study treatment relationship
- Adverse events, suspected to be study treatment related
- Serious adverse events, regardless of study treatment relationship
- Serious adverse events, suspected to be study treatment relationship
- Adverse events leading to study drug discontinuation, regardless of study treatment relationship
- Adverse events leading to study drug discontinuation, suspected to be study treatment relationship
- Adverse events requiring dose adjustment or interruption, regardless of study treatment relationship
- Adverse events requiring additional therapy, regardless of study treatment relationship

- Adverse events which are not serious adverse events, regardless of study treatment relationship

2.11.1.1 Adverse events of special interest / grouping of AEs

Specific groupings of adverse events of special interest will be considered and the number of patients with at least one event in each grouping will be reported. Such groups consist of adverse events for which there is a specific clinical interest in connection with deferasirox treatment. Note that certain adverse events will be reported within multiple groupings/AESIs. AESIs are defined by MedDRA terms. Definition for retrieval (maintenance of terms considered AESI) is in case retrieval strategy (eCRS). To select the corresponding records from SAS dataset ECRS in Novartis computing environment, use

- Compound name = “ICL670”,
- Compound indication = “ICL670 Chronic iron overload”
- and records without CRS Version End Date, means the latest version.

All safety topics flagged in the eCRS using the core safety flag will be considered for the analysis.

AESI will be summarized regardless of study drug relationship, by grouping, preferred term. Gastrointestinal AEs will also be summarized as a part of AESI.

2.11.2 Subgroup analysis

Not Applicable

2.11.3 Deaths

Summaries for on-treatment (treatment +30 days) deaths will be produced by system organ class, and preferred term using the Safety set.

All deaths will be listed for the safety set. If any data after end of treatment plus 30 days is collected, it will be flagged in the listing.

Urinary total protein/creatinine ratio	>1.0 mg/mg at two consecutive measurements at least 7 days apart
Total bilirubin	$>2 \times ULN$
Direct bilirubin	$>2 \times ULN$

Summaries for the change from baseline will be provided for all parameters. Creatinine clearance will be estimated using the (modified) Schwartz formula (additional details in [section 5.2](#)). An unscheduled visit will be mapped to a scheduled visit per [section 2.10.2](#).

Potential Hy's Law events are defined as patients with concurrent occurrence of AST or ALT $> 3 \times ULN$ and TBIL $> 2 \times ULN$ and ALP $< 2 \times ULN$ in the same assessment sample during the on-treatment period. Potential Hy's law events will be tabulated using Safety set.

2.11.5 Other safety data

2.11.5.1 ECG and cardiac imaging data

2.11.5.1.1 Data handling

In case ECG measurements are replicated at any assessment, the average of the ECG parameters at that assessment will be used in the analyses.

2.11.5.1.2 Data analysis

12-lead ECGs including PR, QRS, QT, QTcF and HR intervals will be obtained for each subject during the study as clinically indicated. ECG data will be read and interpreted centrally.

- QT and QTcF
 - New value of > 450 and ≤ 480 ms
 - New value of > 480 and ≤ 500 ms
 - New value of > 500 ms
 - Increase from baseline of > 30 ms to ≤ 60 ms
 - Increase from baseline of > 60 ms
- HR
 - Increase from baseline $> 25\%$ and to a value > 120 bpm
 - Decrease from baseline $> 25\%$ and to a value < 65 bpm
- PR
 - Increase from baseline $> 25\%$ and to a value > 160 ms
 - New value > 200 ms
- QRS
 - Increase from baseline $> 25\%$ and to a value > 80 ms
 - New values of QRS > 120 ms

A listing of all ECG assessments will be produced using Safety set, notable values and post-treatment assessments (if any) will be flagged.

2.11.5.2 Vital signs

Vital sign assessments will be performed in order to characterize basic body function. The following parameters are collected: height (cm), weight (kg), body temperature ($^{\circ}\text{C}$), supine systolic and diastolic blood pressure (mmHg) and supine pulse rate (bpm).

The change from baseline in systolic and diastolic blood pressures, pulse rate, temperature and weight will be summarized by scheduled visit with descriptive statistics. An unscheduled visit will be mapped to a scheduled visit per [section 2.10.2](#).

A listing will be provided for all vital signs and BMI (Body Mass Index). Notable vital signs will be flagged. The criteria for notably abnormal vital signs are displayed in Table 2-2.

Table 2-2 Definition of notable ranges for vital signs

Vital sign (unit)	Notable high value	Notable low value
Weight (kg)	increase $\geq 10\%$ from baseline	decrease $\geq 10\%$ from baseline
Systolic blood pressure (mmHg)	≥ 110 and increase from baseline of ≥ 20	≤ 85 and decrease from baseline of ≥ 20
Diastolic blood pressure (mmHg)	≥ 72 and increase from baseline of ≥ 15	≤ 50 and decrease from baseline of ≥ 15
Pulse rate (bpm)	≥ 120 and increase from baseline of >15	≤ 50 and decrease from baseline of >15
Body temperature (°C)	≥ 40	≤ 35

2.11.5.3 Auditory and ocular findings

Auditory and ocular exams will be performed at screening, EOT and as needed basis. Auditory data will be listed using the Safety set. The listing will include the date when the tests were performed, overall interpretation of the test and any clinical significant abnormality findings.

Ocular data will also be listed using the Safety set. The listing will include the date of assessment performed, overall interpretation and any clinical significant abnormality findings.

2.11.5.4 Hepatic dysfunction

Hepatic dysfunction will be captured through imaging, liver event pathology, liver event by autoimmune disorder, liver serology and liver function tests from the study eCRFs. Due to less number of patients enrolled in the study and considering hepatic cases observed are rare for this compound, no summary will be provided; instead, any findings of hepatic dysfunction will be listed using Safety set.

2.12 Pharmacokinetic endpoints

Not applicable.

2.13 Observer reported outcomes (ObsRO)

There are three set of PRO questionnaires designed to evaluate crushed deferasirox FCT:

- Modified Satisfaction with Iron Chelation Therapy (mSICT) questionnaire
- Palatability (taste and ability to consume medicine) questionnaire
- GI symptom questionnaire

All these questionnaires will be translated in caregivers' native language and will be answered electronically by the caregivers (legal guardian or the parent) at the time of protocol defined visits. The site study personnel will review and will ensure that all relevant observations with parent/ legal guardian are recorded before electronic submission.

2.13.1 mSICT

The mSICT questionnaire will be completed at screening visit 1, week 4, week 12 and EOT. The responses from screening visit 1 for mSICT questionnaire will be considered as baseline. The modified SICT consists of 20 items that represent 3 domains (see Figure 2-1):

- Adherence
- Preference
- Concerns

2.13.1.1 Adherence

Adherence domain will be captured from 2 perspectives:

- Child's perspective (a Domain score + a Checklist for reasons for non-adherence)
- Caregiver's perspective (a Domain score + a Checklist for reasons for non-adherence)

Even the adherence domain is divided into two perspective, all the items will be answered by the caregivers due to minors (2-6 years of age) enrolled in this study. First set of questionnaires will reflect about the child's devotion of taking the medicine and second set of questionnaires will reflect caregivers perspective of adherence for study medication. Out of 20 items of mSICT questionnaire, child's perspective domain scores consist of 6 items (Item: 3, 4, 5, 7, 8 and 9) while caregiver's perspective is captured by 6 items (Item: 13, 14, 15, 16, 18 and 19), i.e. overall 12 items will measure the adherence of the treatment.

Non-adherence items from the child perspective and caregiver's perspective domains consist of one item each (Item: 6) and (Item: 17) respectively.

Child's perspective of adherence:

Item 3 captures about the frequency of medicine intake and **item 5** discusses about how often child follows the doctor's instructions. **Items 3 and 5** will be measured using a 5-point response scale: "Always" =1 (best), "Most of the time" =2, "Sometimes" =3, "Rarely" =4 and "Never" =5(worst).

Item 4 discusses about how often the child express to stop the medication. The scale will be used to measure this as "Always" =5 (worst), "Most of the time" =4, "Sometimes" =3, "Rarely" =2, and "Never" =1 (best).

Two items (**Item 7 and 8**) use different response options. **Item 7** focuses on "How easy/hard did your child tell you it was to take his/her medicine" and uses the response scale "Very easy" =1 (best), "Easy" =2, "Neither easy or hard" =3, "Hard" =4, and "Very hard" =5 (worst). Similarly, **item 8** captures bother expressed by child for amount of time he/she had to wait to eat food after taking medication. The response scale for Item 8 will be "Very bothered" =5 (worst), "Quite Bothered" =4, "Moderately bothered" =3, "A little bothered" =2, and "Not bothered at all" =1 (best).

Item 9 reports “how happy your child appeared” and is scored on a scale from 1=Very happy (best) to 5=Very unhappy (worst).

[figure not shown]
Caregiver's perspective of Adherence:

Item 13 asks the caregivers about how often medicine is given to the child and **item 15** asks about how often caregivers follow doctor's instruction for giving child his/her medicine. **Item 13** and **15** both are measured using a 5-point response scale: “Always” =1 (best), “Most of the time” =2, “Sometimes” =3, “Rarely” =4 and “Never” =5 (worst).

Conversely, **item 14** will capture the caregiver perspective about “how often he/she thought of stopping the medicine”. **Item 14** will be scored as “Always” =5 (worst), “Most of the time” =4, “Sometimes” =3, “Rarely” =2, and “Never” =1 (best).

Item 16 and **18** focus on “how easy/hard was it to crush the medicine” and “How easy/hard was it to give your child his/her medicine” respectively and use the same response scale “Very easy” =1 (best), “Easy” =2, “Neither easy nor hard” =3, “Hard” =4, and “Very hard” =5 (worst). Similarly, **item 19** captures “bothered by the amount of time it took to prepare medication” and uses the response scale “Very bothered” =5 (worst), “Quite Bothered” =4, “Moderately bothered” =3, “A little bothered” =2, and “Not bothered at all” =1 (best).

Figure 2.1 Proposed Conceptual Models for the Modified Satisfaction with Iron Chelation Therapy Questionnaire

Adherence Domain Score Calculation

[figure not shown]
A separate adherence domain scores for the child's and caregiver's perspective will be calculated. A domain score will be calculated by summing item scores on respective domains. Overall, a lower domain score will indicate better adherence. Note that **Item 6 and 17** will be analyzed separately and thus will not be included while calculating caregiver's perspective for adherence, i.e. it will not be included in the summation.

Child's Perspective and Caregiver's Perspective Checklist for Non-adherence

Only respondents who, at **item 5** (for the child's perspective) and **item 15** (for the caregiver's perspective), indicate that they did not "Always" take their medication as instructed, are expected to give the reasons for non-adherence. For both the "child's perspective of adherence" and "caregiver's perspective of adherence," there is an item to capture the reasons for non-adherence, where the respondent can check all the reasons that apply.

From the child's perspective, **item 6** ("reason expressed by your child for not always taking the medicine as instructed by the doctor") and **item 17** from the caregiver perspective ("reason that you did not always give your child his/her medicine as instructed by the doctor") capture the reasons for non-adherence. These response options are treated as a standalone checklist, which captures the child's and caregiver's perspective on the reasons why the child did not always take their medication as instructed. See **Figure 2.2**

Figure 2.2 Conceptual models for item 6 and item 17 of the modified SICT

This item will be used as a standalone item to further understand the overall Adherence domain and the responses will be presented descriptively using frequency counts.

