These dosing tables have been constructed for each dosing group considering lower (5th) and upper (98th) percentiles from weight charts for children aged ≥ 2 to < 6 years. This is taking into account that the study will enroll male or female children, ≥ 2 and < 6 years. For patients with a low body weight and lower daily DFX dosing requirements (e.g. below 19 kg body weight in the 3.5 mg/kg/day dosing group) the needs will not allow for the use of the smallest tablet strength available. In such cases a written request will be sent to Novartis, to advise on the individual patient enrolment / dose adjustments options.

The patient will be dispensed deferasirox FCT in accordance with the protocol. For patients already well-managed on prior treatment with deferoxamine or deferasirox DT, a starting dose of crushed deferasirox FCT is outlined below in [Table 6-2](#).

Table 6-2 Equivalent dose of deferasirox FCT

ICT Dose Prior to Enrollment	Starting Dose		
	Deferoxamine (mg/kg/day)	Deferasirox DT (mg/kg/day)	Deferasirox FCT (mg/kg/day)
10	5	3.5	
20	10	7	
30	15	10.5	
40	20	14	
50	25	17.5	

Dose equivalence between deferiprone and deferasirox has not been established in clinical studies. For patients pre-treated with deferiprone, the starting dose of deferasirox FCT should be 14mg/kg/day.

Safety assessment will be performed weekly after treatment initiation and thereafter monthly during the study. Monthly serum ferritin values and trends will be used to adapt the treatment of the patients together with safety data.

Patients will continue therapy for 24 weeks.

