7.2.8 Patient reported outcomes

As detailed in [Table 7-1](#) and provided in Appendix 14.1, patients or their caregivers will complete a series of ObsRO questionnaires at the study site (during study visits) as follows:

- palatability and mSCIT of crushed FCT, at SV1 and at the following visits: week 4, week 12 and at end of treatment
- gastrointestinal symptoms of crushed FCT at SV1 and at the following visits: week 2, week 3, week 4, week 8, week 12, week 16, week 20 and at end of treatment

Note: Chelation naïve patients and patients treated with chelation therapy who stopped treatment more than 7 days prior to Screening visit 1 will not complete questionnaires at screening.

8 Safety monitoring and reporting

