15. Over the past week, how often did you follow the doctor's instructions for giving your child his/her medicine for iron overload?

- Always
- Most of the time
- Sometimes
- Rarely
- Never

16. Based on doctor's instructions, how easy or hard was it for you to crush the tablet for iron overload?

- Very easy
- Easy
- Neither easy nor hard
- Hard

Very hard

17. What are the reasons that you did not always give your child his/her medicine for iron overload as instructed by the doctor? (Choose all that apply)

- Child refused to take
- Forgot to give the medicine
- Inconvenient for you or your child
- Side effects (for child)
- Did not prepare the medicine according to the doctor's instructions
- Did not give the full amount of the prepared medicine
- Other _____

18. Over the past week, how easy or hard was it for you to give your child his/her medicine for iron overload?

- Very easy
- Easy
- Neither easy nor hard
- Hard
- Very hard

19. Over the past week, how bothered were you by the amount of time it took to prepare your child's medicine for iron overload?

- Very bothered
- Quite bothered
- Moderately bothered
- A little bothered
- Not bothered at all

20. Please rank order the following medicines based on what your children most prefers to what he/she least prefers.

Medicine	Rank (1= most prefer and 6= least prefer)
Tablet to dissolve in liquid	
Tablet (taken once a day)	
Tablet (taken 3 times a day)	
Tablet crushed	
Sprinkle powder on food	
Injection	

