2.13.1.3 Concerns

Similar to adherence domain, concerns will be captured 2 ways:

1. based on the child’s perspective (**Item 1 and 2**) and
2. also based on the caregiver’s perspective (**Item 12**)

The concerns domain for the child’s perspective has 2 items which focus on “limiting child’s activity” (**Item 1**) and “getting upset about the side-effects” (**Item 2**). Both the items are measured using a 5-point response scale from “Always” =1 (worst), “Most of the time” =2, “Sometimes” =3, “Rarely” =4, and “Never” =5 (best); and a sum of scores for a Concerns domain for the child’s perspective will be created if both items are non-missing. A higher score will indicate lesser concerns.

There is only a single item to capture concern in regards to caregiver’s perspective. The **item 12** captures about “how worried whether the child is swallowing enough medication” and is scored on a 5-point response scale from “Always” =1 (worst), “Most of the time” =2, “Sometimes” =3, “Rarely” =4, and “Never” =5 (best). A higher score on the single item domain will indicate lesser caregiver concern.

For the mSICT questionnaire, the score for each domain (adherence and concerns) will be the mean of the score of items included in the corresponding domain. Note that for these domains, child’s perspective and caregiver’s perspective will be summarized separately. Standard descriptive analyses will be performed for each domain (adherence and concerns) score at screening visit 1 (baseline), week 4, week 12, and end of treatment visits, as well as their changes from baseline at week 4, week 12, and end of treatment for pre-treated chelation patients where baseline evaluation is available. For the Chelation naïve patients and patients treated with chelation therapy other than deferasirox who stopped chelation treatment more than 7 days prior to Screening visit, only descriptive statistics by visit will be provided. The standard descriptive analyses include: n, mean, standard deviation, minimum, median, and maximum. The 95% confidence intervals will be presented for the changes in mean from baseline for all domains at week 4 and week 12 and EOT for patients pre-treated with deferasirox only.

Box plot will be presented to summarize the scores graphically for each domain at week 4, week 12 and EOT.

All preference items will be analyzed descriptively by visit.

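### Caregiver adherence score counts ease of crushing (item 16), which has no meaningful SV1 answer where the prior chelator was not crushed, so change from baseline is not like-for-like for those families

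*SAP*

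**What the plan says.** - **Items.** SAP 2.13.1.1 builds the caregiver adherence score from six items, item 16 among them: "perspective is captured by 6 items (Item: 13, 14, 15, 16, 18 and 19"). Each is scored 1 (best) to 5 (worst).
- **Item 16.** In the mSICT form (Protocol Appendix 14.1) it asks "how easy or hard was it for you to crush the tablet for iron overload". The five printed answers run from very easy to very hard, and none allows for a medicine that was not crushed.
- **Baseline.** SAP 2.13.1: "The responses from screening visit 1 for mSICT questionnaire will be considered as baseline". Protocol 7.2.8 schedules "palatability and mSCIT of crushed FCT, at SV1 and at the following visits: week 4, week 12 and at end of treatment", and no separate baseline form is shown. Table 7-1 has the first dispensing of study drug at Week 1 Day 1.
- **Prior chelators.** Protocol 6.1 gives starting doses thus: "For patients already well-managed on prior treatment with deferoxamine or deferasirox DT". It also covers children who were on deferiprone. In mSICT items 10 and 20, "Tablet to dissolve in liquid" and injection are listed separately from a crushed tablet.
- **Scoring.** SAP 2.13.1.1: "A domain score will be calculated by summing item scores on respective domains". SAP 2.13.1.3 and Protocol 10.5.7 instead define the domain score as the mean of its items.
- **Analysis.** SAP 2.13.1.3 summarises domain scores by visit, "as well as their changes from baseline at week 4, week 12, and end of treatment for pre-treated chelation patients", provided a baseline evaluation is available. It limits the 95% confidence interval for the change to patients pre-treated with deferasirox.
- **Missing items.** A condition is stated for the child Concerns score (both items must be present). None is stated for either adherence score.

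**The concern.** At SV1 the caregiver is rating the previous chelator. Items 13, 14, 15, 18 and 19 (giving it, thinking of stopping, following instructions, ease of giving, preparation time) can be answered for any chelator. Item 16 can be answered only for a tablet that was crushed. From Week 4 every caregiver can answer it, because crushing is mandatory. For a family that crushed nothing before entry, the baseline and follow-up scores therefore do not measure the same thing, and the SAP does not say what happens to the SV1 score.

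Treatment satisfaction is a stated secondary objective. In a single-arm study, change from SV1 is the only within-trial contrast for it. Crushing is also the feature of this formulation that the study was set up to examine, so its burden should be visible in its own right and not mixed into a change score with a non-equivalent baseline.

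**Working it through.** The plan states no figure for this score that could be reproduced. One count can be checked: six child items (3, 4, 5, 7, 8, 9) plus six caregiver items give the 12 adherence items that SAP 2.13.1.1 states.

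**Inputs**
- m: mean of the five common items (13, 14, 15, 18, 19), between 1 and 5, held equal at SV1 and follow-up so that there is no true change.
- x16: item 16 at follow-up, 1 (very easy) to 5 (very hard).
- b16: an SV1 answer to item 16, if one is given.
- Score range: 6 to 30 for a six-item sum, 5 to 25 for a five-item sum, 1 to 5 for a mean.

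**Four ways of handling item 16 at SV1; the documents do not choose between them**

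1. *Blank, available items summed.* Artefact = (5m + x16) − 5m = x16, so +1 to +5. It is always towards worse adherence, even when crushing is very easy.
2. *Blank, available items averaged.* Artefact = (5m + x16)/6 − m = (x16 − m)/6. The extremes are (1 − 5)/6 = −0.67 and (5 − 1)/6 = +0.67. The sign depends on whether crushing scores better or worse than the other items.
3. *Blank makes the score missing.* There is no change score for the family. The analysis keeps only families who gave an answer to item 16 at SV1.
4. *An answer is forced.* Artefact = x16 − b16, from −4 to +4, on the sum; (x16 − b16)/6, from −0.67 to +0.67, on the mean.

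**Example for cases 1 and 2:** all five common items scored 2 at both visits (m = 2)

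| Item 16 at follow-up | Sum, SV1 to follow-up | Artefact | Mean, SV1 to follow-up | Artefact |
|---|---|---|---|---|
| 1 | 10 to 11 | +1 | 2.00 to 1.83 | −0.17 |
| 2 | 10 to 12 | +2 | 2.00 to 2.00 | 0 |
| 4 | 10 to 14 | +4 | 2.00 to 2.33 | +0.33 |
| 5 | 10 to 15 | +5 | 2.00 to 2.50 | +0.50 |

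The same answers can therefore look like a clear worsening under one rule and no change, or a slight improvement, under the other.

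**Group level.** If a share f of the children with a change score is affected, the mean change carries f times the average artefact among them in cases 1, 2 and 4. The documents give no value for f, so it can lie anywhere from 0% to 100%.

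**With item 16 left out of the change score.** The artefact is 5m − 5m = 0 on the sum and m − m = 0 on the mean, whatever was entered at SV1.

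**The case against.** The strongest reply is that neither the size nor the direction of any distortion is fixed by the documents.

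- The mean rule appears in the protocol and again in SAP 2.13.1.3; the sum appears only in SAP 2.13.1.1. Under the mean the artefact can go either way and can be zero.
- The SAP makes a value missing when a component is missing for child Concerns and for serum ferritin change. Applied here, that would cost sample size without creating a five-versus-six comparison.
- Table 6-2 converts doses; it is not a list of what children were taking. FCT is marketed in some participating countries, the EU label allows crushing, and children continuing on deferasirox are eligible. Some may already have been taking crushed FCT.
- The documents do not say how deferiprone tablets were given to such young children, so crushing cannot be excluded.
- The documents do not show whether the electronic form lets a caregiver skip the item.

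All of this stands, and it rules out a stronger reading that a reader might infer: that the plan builds in a spurious worsening for every pre-treated child, with a confidence interval around it. A certain worsening needs the sum rule together with a choice to ignore blanks, which is nowhere stated. Children already on crushed FCT are compared like-for-like. Under the SAP, deferoxamine and deferiprone families can enter the descriptive change but not the interval.

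The reply does not remove the structural problem. None of the four ways of handling item 16 gives an affected family a like-for-like six-item change. Requiring an available baseline evaluation does not settle the matter either, because the SAP does not say whether a form with item 16 blank counts as available.

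**Conclusion.** The point holds as a structural one: for families whose earlier chelator was not crushed, the caregiver adherence change from SV1 is not like-for-like, and the SAP has no rule for it. The distortion in an affected child's score is bounded as shown above. Those bounds assume no true change in the five common items, and they depend on a scoring rule that the SAP states in two ways and on a treatment of blanks that it does not state.

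The descriptive change for all pre-treated children with a baseline is exposed. The confidence interval is exposed only as far as deferasirox-treated children were not already taking crushed tablets. Chelation-naive children are outside the problem, since they have no SV1 questionnaire and no change score. The primary gastrointestinal endpoint and the sample size are unaffected. This is one item of six in a descriptive secondary outcome: worth correcting because correction is cheap, but not a threat to the study's main conclusion.

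**What to change.** In SAP 2.13.1.1 and 2.13.1.3:

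1. Compute change from SV1 in caregiver adherence from items 13, 14, 15, 18 and 19 only.
2. Choose one scoring rule for the domain, reconciling the sum in 2.13.1.1 with the mean in 2.13.1.3 and Protocol 10.5.7, and add a missing-item rule for both adherence scores.
3. Report item 16 on its own by frequency counts at Week 4, Week 12 and end of treatment. The SAP already keeps items 6 and 17 outside the score in this way.
4. If a six-item score is kept, show it post-baseline only. Those are the visits already chosen for the box plots.

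The cost is SAP wording and one changed derivation, with no new data. The downside is that the change score rests on five of the six items; the sixth is still reported.
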